7.3 Indicators for Objective 3: Enhance disease surveillance and outbreak detection

- Number of M&E and HMIS indicators based on individual data that can be visualized through the medAL-outbreak dashboard
- Average delay between the date of recording of clinical data and the date they are available on medAL-outbreak
- Number and type of epidemic alerts raised by medAL-outbreak
- % of these epidemic alerts registered by the district authorities for epidemic response

7.4 Indicators for Objective 4: Enhance M&E and supportive supervision and mentorship

- Number of M&E indicators based on individual data that can be visualized through the medAL-monitor
- Number of supervision and mentorship visits to HFs facilitated by medAL-monitor
- Number of HCWs reporting having used medAL-monitor for self-auditing their clinical practices
- Number of HCWs and members of CHMT reporting a positive experience with medAL-monitor

7.5 Indicators for Objective 5: Create a supportive environment for the use of clinical algorithms and disease surveillance tools

- Number of sick children attending primary care facilities managed by HCWs using the electronic ePOCT+ tool
- % of HCWs able to assess key clinical signs
- Frequency of use of medAL-outbreak by district team members
- Frequency of use of the medAL-monitor tool by district team members
- Perception by HCWs of the ePOCT+ tool and intervention and the number of improvements they propose for the tool or intervention
- Perception by caregivers and community members of the intervention and the number of improvements they propose
- Perception by district team members of medAL-monitor/medAL-outbreak and the number of improvements they propose for the tool
- Number of medical experts able to modify a clinical algorithm using MedAL-Creator

- Number of computer scientists able to maintain the software and the IT infrastructure for clinical algorithms
- Number of scientists able to analyze clinical data using ML
- Number of local students trained in applied ML for health care in resource-limited settings
- Perception of the current and future utility of ML to improve health care amongst clinical experts (deciding on algorithm changes) and health authorities
- Patient and provider expenditures related to care of acutely ill children included in the study
- Carbon footprint of the intervention or carbon-saving due to the intervention

8 STUDY PROCEDURES

8.1 Objective 1: Improve the integrated management of sick children

8.1.1 Recruitment, screening and informed consent procedure

As the intervention is implemented at the facility level, approvals from relevant authorities will be sought before engaging with persons in charge of HFs and HCWs. Sensitization meeting will be organized in the villages or suburban wards within the catchment areas of enrolled HFs. District and HF consent will be obtained for the intervention. HFs will be informed if they have been allocated to the intervention or control group and that, if allocated to the control group, they will benefit from the intervention a maximum of one year after the start of implementation, until at least the end of year 2022. Individual consent from caregivers will be sought for electronic recording of data and follow-up by phone call or SMS. Upon the start of the study, information will be provided in the waiting areas of facilities.

All children aged 1 day to 14 years presenting for an acute problem during or after working hours to a HF that is part of the study will be asked if they wish to participate in the study by the person usually doing registration of patients (using the registration module in the tablet) or another appropriate staff member trained in ascertaining consent. The consent process will be integrated into the routine work flow at the health facility. Caregivers will be asked consent for electronic data recording and follow-up by phone or SMS for their child. They will be informed that not providing consent will not affect the medical management of their child and, in intervention facilities, the child can still benefit from being managed by the ePOCT+ tool and that their data will not be used for research purposes. All caregivers will be provided a paper-based participant information sheet and consent form providing sufficient information to make an informed decision about their participation in the study. If the clinical condition of the child requires immediate treatment, this will supersede the written consent process, which will be conducted once the child is stabilized. The consent form will be retained as part of the study records.

After the completion of the Phase 1 study, if the benefits of the intervention are confirmed, in the routine implementation of ePOCT+ the individual consent process will be simplified (consent at district and health facility level will be maintained). District and health facility level consent (obtained in sequence) will be documented on the same consent form and copies will be kept at district level, health facility level, and with the investigators. The registration form will be reduced and integrated into the routine registration process. Consent will be limited to a verbal agreement that data recorded in the tablet during the consultation can be used for research. Ticking “yes” in the application means that consultation data will be sent to the research database. Ticking “no” means that the data will remain on the tablet/local data server and will not be analysed. Otherwise, all children will be treated in the same way (using the tablet). In case of any significant modifications in the algorithm content that require validation using a sub-study, in health facilities participating to the sub-studies, written consent procedure as outlined in Phase 1 will be maintained. Patients participating in the surveillance

[figure not shown]
sub-study will also undergo the full written consent process.

8.1.2 Management of sick children during the initial consultation

In HFs with dedicated staff for triaging patients, sick children will first be assessed by this person using the triage module of ePOCT+ in the tablet. If the child requires urgent treatment, the triaging person will immediately inform the attending HCW(s), so that she or he can give priority to that child over others waiting to be seen. If not, the child will queue normally and be attended by the next available HCW. As part of triage, the vital signs will be measured (temperature, respiratory rate, weight and MUAC) as well as, if the child fulfils certain clinical criteria, oxygen saturation and cardiac rate using the pulse oximeter. If there are no dedicated triage staff, the triage module will be deactivated and vital signs will be measured during the consultation.

The attending HCW will either manage the child using the ePOCT+ algorithm (in intervention facilities) or as per routine (in control facilities). If the child needs to go to another room for laboratory investigations (rapid tests or other), the HCW will be able to suspend the ePOCT+ algorithm and data recording in the tablet and attend another child in the meantime, opening a parallel session in the tablet. When the child returns with the test results, the HCW will resume the ePOCT+ algorithm and data recording of that child and continue the consultation normally. At the end of the consultation, the HCW, in both intervention and control facilities, will be asked to enter the final decision on referral, tests performed, final diagnoses and treatments prescribed (see chapter 8.1.6 on outcomes measurements). After the consultation, this information will be synced to the server at IHI offices as soon as there is internet connectivity.

Figure 9: Flowchart of health facilities and patients included in Phases 1 and 2

8.1.3 Re-attendance visits in case of persisting or worsening of symptoms

At initial consultation, the advice to caregivers on when to bring the child back to the HF is left at the discretion of the HCW. In intervention facilities, HCWs will be guided by the ePOCT+ tool, which recommends conditional follow-up based on WHO and national guidelines.

At re-attendance visits, whether scheduled or unscheduled, children will be managed according to the study arm to which they were initially assigned (ePOCT+ or routine care) in Phase 1, and with the support of ePOCT+ for all children in Phase 2. In case children still present fever at day 7, the algorithm will recommend in all cases to give an antibiotic to cover the possibility of an undetected bacterial infection. If surveillance laboratory results show that the child was suffering from a rare bacterial infection not covered by the antibiotic provided at day 7 (e.g. rickettsiosis or leptospirosis), the caretakers will be contacted to ensure that the child is indeed cured. If the child is still or again sick, caretakers will be asked to bring the child to the health facility to be assessed clinically and receive the necessary specific antibiotic.

If the child comes back to the same HF as for the initial consultation, the HCW will have access to the electronic data of that initial consultation that is saved in the HF tablets. If the child goes to a different HF that is participating to the study, the HCW will not have access to that data. Investigators will however be able to link data collected at different facilities (as long as they are part of the study) for a same child through the unique identification number provided to caregivers. If the child goes to a HF not participating in the study, no data will be available for that consultation. The ePOCT+ registration module, used at all participating facilities, will inquire about the type of visit (initial / scheduled re-attendance / unscheduled re-attendance) and the main reason for that visit.

8.1.4 Training of health providers on how to use ePOCT+

In intervention facilities, HCWs will participate in centralized in-person 3-day training course. They will receive general training on the epidemiology of diseases in Tanzania, the most important pediatric diseases and their clinical predictors, the content of the ePOCT+ algorithm and the importance of rational antibiotic and antimalarial use. General, key clinical skills will also be reviewed during this training and an introduction to the e-learning tool aimed at supporting these skills once they return to their facilities will be given. In addition, HCWs will receive training on how to use the ePOCT+ application on the tablet, using clinical case studies, as well as job aids for conducting and interpreting the results of POC tests which are not currently part of standard care at PHC level but are included in the algorithm (e.g. pulse oximetry and CRP rapid test).

During the month following this centralized training, HCWs will benefit from one visit for in-service face-to-face training during which trainers will accompany them in some of their consultations with real patients and help them optimize the way they use ePOCT+. Trainers will also support reorganization of workflows in the HF if necessary.

At the end of Phase 1, all HCWs from control HFs as well as those from the new participating facilities will receive the same training as described above. During both Phases 1 and 2, new personnel at study facilities will be trained through a dedicated module on the tablet and by their peers. This module will be available to all HCWs using ePOCT+ so that they can refresh their knowledge any time.

8.1.5 Supervision of health providers by the CHMT

The CHMT will be provided the medAL-monitor tool which is a dashboard available on PCs and tablets allowing them to monitor indicators (see **Table 3**) related to pediatric consultations taking place in the HFs enrolled in the study. Data on the child's or the HCW's identification will not be provided, only the name of the health facility will be available. Based on these indicators, the supervision team will be able to better organize on-site visits to HFs, prioritizing the lowest performing ones, knowing in advance what areas of improvement to concentrate on. As the persons in charge of HFs, as well as

each HCW, will also have access to these indicators (fully anonymized except for their own data) to allow them to do self-auditing at HF level so that they are aware of their own performance in advance of receiving a CHMT supervision visit. The aim of the medAL-monitor tool is to stimulate HCWs' motivation and self-leadership to improve their skills and competencies, while enabling the supervision team to help them resolve remaining problems (Bessat et al. 2019).

8.1.6 Type of care, training and supervision provided at intervention and control facilities

In intervention HFs, HCWs will be guided by the ePOCT+ recommendations throughout the consultation. However, health care providers are ultimately responsible for the clinical management of all patients and may override recommendations of the algorithm and provide additional or withhold treatment according to their own clinical judgement. All concomitant diagnostic interventions and treatments will thus be left at the discretion of the provider but recorded in the ePOCT+ tool. In control HFs, routine care as currently implemented in Tanzanian primary care settings will be provided. Before the start of Phase 1, all skilled HCWs who are engaged in triage, assessment, and medical management of sick children in both intervention and control facilities will receive training in study-related procedures, including consent for electronic recording of data, and documentation of the final decision on referral, tests performed, final diagnoses and treatments using the tablet. In intervention HFs, training on the ePOCT+ tool will be provided as described above while in control facilities, standard paper guidelines (IMCI and Tanzanian national treatment guidelines) will be provided and HCWs reminded that these guidelines should be followed during patient management. They will also be informed that, after the end of phase 1, they will receive the intervention exactly as HCWs of initial intervention HFs did.

In intervention HFs, HCWs will receive feedback on the data registered through the ePOCT+ tool, and the CHMT will be using medAL-monitor to better target supervision and support to facilities. In control facilities, supervision by the district team will be done using the available DHIS2 data as usual.

In both intervention and control facilities, it is assumed that usual diagnostic tests and treatments will be provided through the routine health care system. Control HFs will not receive additional POC tests that HFs in Tanzania would not normally have available in similar settings (i.e. CRP test). Care for children under the age of five years is free of charge while caregivers are expected to pay out of pocket for health care expenses of older children (unless expenses are covered under an insurance policy). However, when not available at the HF, patients must procure their medications from nearby pharmacies or other HFs. To allow testing of the intervention under conditions as close as possible to those expected for future implementation, we will not provide routine diagnostics or medications in either intervention or control facilities. However, we will ensure that immediate life-saving treatments are available and will support the facility staff in managing stocks through routine mechanisms.

8.1.7 Measurement of primary and secondary outcomes

Data captured on the tablets used by health care workers during the consultation

During the pilot phase before Phase 1 begins, tablets will be provided to HCWs in both intervention and control HFs. In intervention HFs the tablets will contain the patient registration module followed by the ePOCT+ algorithm that will guide them throughout the consultation process. In control HFs, tablets will only collect the patient demographics (see **Appendix 1**).

To determine the percentage of children prescribed an antibiotic or an antimalarial, as well as to know the final decision on referral and final diagnoses retained by HCWs, four questions will appear on the screen at the end of the consultation process, i.e. once the clinician has gone through the entire algorithm in intervention HFs or just after the patient registration module in control HFs. HCWs will be asked to document the final decision regarding the need for referral, tests performed and the results, decision on the date of follow-up (if needed), final diagnoses and final treatments prescribed. For each

medicine prescribed, the dosage and duration of the treatment will also be recorded (see **Appendix 1**).

Data captured through phone calls or home visits (Phase 1) or automated phone calls or SMS (Phase 2) to caregivers

For Phase 1, research assistants will be trained to administer a simple questionnaire by phone to caregivers of all children at day 7 (range 6-14) after their initial consultation with a HCW of participating facilities, regardless of re-attendance visits. If the phone follow-up fails, up to four additional attempts will be made on the subsequent days, after which they will be deemed lost to follow-up. These research assistants will be placed outside HF and blinded to which facility the child has attended as much as possible. Data recorded during these phone interviews will be collected electronically and sent at least once a day to the central server of the study at IHI. For the question related to the clinical primary outcome measure (percentage of children cured at day 7), field workers will be particularly trained not to influence caregivers when they answer the questions "Is the child cured?" and insist that they simply answer by "Yes" or "No". If the answer is "No", the caregiver will be strongly advised to re-attend a HF, if possible, the one they went to for the initial consultation. Same procedure will be implemented if home visits are required using a REDCap mobile application. The questions included in the phone questionnaire are listed in **Appendix 1**.

During Phase 2, instead of a phone call, only caregivers of children participating to the sub-studies will receive a phone call or an automated SMS or automated phone call on day 7 with the same questions as in the questionnaire used in Phase 1. The automated follow-up system will be tested during Phase 1 in parallel with phone calls in a subset of patients, to check for congruency between the answers obtained by a caller and by automated voice message or SMS.

In Phases 1 and 2, when the participant reports that the family has no phone number, or no response is received from the phone call or SMS, the field assistant may make a physical follow up to ascertain the responses of several unanswered contact attempts with support of the local village leaders as key informants.

Data captured during the three cross-sectional quality of care surveys

Research clinical observers who have been trained on the study procedures will visit randomly selected HF. They will ask HCWs present on that day for permission to observe a series of consecutive consultations. They will then ask the HCW to request oral permission from their patient and to sign a consent form indicating their own and the patient's consent to have an observer in the room. Observers will then record, using an electronic questionnaire, key symptoms (danger signs, main exposures and main symptoms) and signs (vital signs, main signs according to the child's main symptoms) assessed by HCWs, diagnostic tests requested, final decision on referral, final diagnoses retained, treatments prescribed and main information and advice given to caregivers. Observers will be trained not to interfere at all with the consultation process; only values of vital signs can be asked to the HCWs if necessary, to be recorded precisely by the observer.

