These measures or indicators include the evaluation of the effects of the use of ePOCT+ (versus routine care in Phase 1; over time and across geographical areas in Phase 2) for managing sick children aged under 15 years presenting to PHC facilities on:

Unscheduled secondary consultations:

- % of children with one or more unscheduled re-attendance visits at any HF by day 7

Severe outcome by day 7:

- % of children with non-referred secondary hospitalization by day 7
- % of children who have died by day 7

Primary referrals:

- % of children referred to hospital or admitted to inpatient ward at a health centre at initial consultation
- % of children who were hospitalized among those referred (i.e. referral completed)

Appropriate case management for malaria at initial consultation

- % of febrile children tested for malaria
- % of malaria positive children prescribed an antimalarial
- % of malaria negative children prescribed an antimalarial
- % of untested children prescribed an antimalarial

Appropriate case management for other conditions at initial consultation

- % of key symptoms and signs checked and diagnostic tests performed by HCWs
- Distribution of final diagnoses (including their severity) made by HCWs
- Concordance between treatment prescribed and final diagnoses made by HCWs
- Concordance between final diagnoses as proposed by ePOCT+ and final diagnoses by HCW (*intervention HFs only*)

Definitions used for the outcome measures and indicators of objective 1

- Clinical cure is a positive answer to the question “Is the child cured?” OR “Has the child improved?” (if not cured) asked to caregiver through a phone call (or home visit) at day 7. Non-referred secondary hospitalizations (see definition below) will however be considered as clinical failures even if the child is already cured at day 7.
- Initial consultation is the first visit of a sick child for an acute problem at a HF participating in the study (and thus registered electronically); timeframe from completion of the initial visit up to midnight of the same day.
- Re-attendance visit is a consultation (not necessarily at a HF participating in the study) taking place from the day after initial consultation up to day 7 included. A re-attendance visit can be scheduled (proposed by the HCW on a certain day) or unscheduled (upon decision by caregivers).

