- Primary referral is a decision of referring the child to hospital taken by the HCW at the initial consultation - Secondary referral is a decision of referring the child to hospital taken by the HCW during a re-attendance visit taking place from the day after initial consultation up to day 7 included.
- Primary hospitalization is an admission to a hospital ward taking place the same day as the initial consultation
- Secondary hospitalization is an admission to a hospital ward taking place from the day after initial consultation up to the phone call at day 7 included. A non-referred secondary hospitalization is a direct visit to hospital without a re-attendance visit the same day at a HF participating in the study.
- Antibiotic prescription is any oral, intramuscular or intravenous (but not topical) antibiotic prescribed by a HCW during the initial consultation or a re-attendance visit
- Antimalarial prescription is any oral, rectal, intramuscular or intravenous antimalarial prescribed by a HCW during the initial consultation or a re-attendance visit
- Febrile child is a child with a history of fever and/or a high temperature
- Malaria testing is a malaria RDT or microscopy ordered by a HCW during an outpatient visit
- Day 7 is a range of 6-14 days post initial consultation to allow for completion of home visit for children whose caregiver reports having no phone / no phone number.

Additional longitudinal analyses:

- Change in % of children prescribed an antibiotic over time
- Change in % of children with basic anthropometrics and clinical signs measured over time (intervention arm only)
- Change in % of consultations where ePOCT+ was used over time (intervention arm only)

7.2 Indicators for Objective 2: Improve the algorithm and adapt it to spatiotemporal variations

- Number of positive impact modifications in the algorithm identified by ML-based analyses
- Number of positive impact modifications tested through randomized sub-studies
- % of these positive impact modifications confirmed to be safe and useful by randomized sub-studies
- Number of modifications implemented by type of impact (better clinical cure, less severe clinical outcomes, less medicines or diagnostic tests needed, shorter consultation time...)

Definitions used for the indicators of objective 2

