Effect modification of the primary outcome of antibiotic prescription of the primary endpoints will be performed in groups of patients where the highest reduction in antibiotic prescription is expected, and areas of extension of the content of the algorithm compared to the version tested in the previous ePOCT study. Effect modification by sex, age groups (young infants ages 1 to 59 days, children aged 2 months to 5 years, and children aged 5 to 14 years), respiratory symptoms, fever without clinical source, gastrointestinal complaints (vomiting and diarrhea), skin problems, ear and throat problems, anemia, and malnutrition will be assessed by incorporating an interaction between arm and the respective variable, acknowledging that power will be low. All models will be adjusted for clustering and the stratification factors (Kahan et al. 2012). Primary analyses will be complete case; we may adjust for further baseline variables which are associated with missing outcome data (which is analogous to performing multiple imputation in the case of a single endpoint). Further details will be provided in the statistical analysis plan.

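### The protocol names no common source for fever status or the clinical effect modifiers in the two Phase 1 arms, so malaria testing in febrile children and most planned interactions would rest on differently ascertained groups

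*Protocol*

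**What the plan says.** **Control-arm capture.** Protocol Section 8.1.7 says "In control HFs, tablets will only collect the patient demographics" and points to Appendix 1. The closing screens follow in both arms: "HCWs will be asked to document the final decision regarding the need for referral, tests performed and the results", then follow-up date, diagnoses and treatments. They appear after the whole algorithm in intervention facilities, but "just after the patient registration module in control HFs".

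**Registration.** Section 8.1.3 adds one complaint item for everyone: "The ePOCT+ registration module, used at all participating facilities, will inquire about the type of visit" "and the main reason for that visit".

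**What the analysis needs.** Section 7.1 lists the percentage "of febrile children tested for malaria" as a Phase 1 secondary outcome and defines the denominator: "Febrile child is a child with a history of fever and/or a high temperature". Section 10.3 plans effect modification of antibiotic prescription by sex, age group, respiratory symptoms, fever without a clinical source and gastrointestinal complaints. The list ends: "skin problems, ear and throat problems, anemia, and malnutrition will be assessed by incorporating an interaction between arm and the respective variable".

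**Other relevant text.** The synopsis (Procedures and measurements) says the control application records outcome-related data on an electronic form. It gives two sources for consultation quality: tablets for referral, tests, diagnoses and treatment, and survey observers for symptoms and signs. Section 8.1.2 describes triage measurement of temperature, respiratory rate, weight and MUAC before it separates the arms, but through the ePOCT+ triage module, which can be switched off.

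**The concern.** A between-arm percentage is interpretable only if its denominator is assembled in the same way in both arms. In intervention facilities the algorithm asks about fever and symptoms and prompts measurements. In control facilities, on the protocol's description, fever can be recognised only from the main reason for the visit, from a test having been done, or from a final diagnosis.

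Tests and diagnoses are poor substitutes. A child known to be febrile because a malaria test was ordered is by construction a tested child. The distribution of final diagnoses is itself a between-arm secondary outcome in Section 7.1, so it arises after randomization and is expected to shift with the intervention.

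Anemia is the clearest case among the modifiers. Table 2 prompts hemoglobin testing in febrile children up to 5 years, and in older children with malnutrition or pallor. Its footnote lists hemoglobin cuvettes among the items the project supplies rather than those routinely available, and Section 6.1 places non-standard tests in the intervention arm. A control child labelled anemic is therefore likely to be more visibly ill than an intervention child with the same label. Prompted weight and MUAC raise the same issue for malnutrition. An arm-by-subgroup interaction would then partly reflect who was detected.

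**Working it through.** **1. Text set side by side**

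| Item needed in both arms | Intervention tablet | Control tablet, as described |
|---|---|---|
| Fever history, temperature | Algorithm | No field named; main reason for visit only |
| Respiratory, gastrointestinal, skin, ear/throat | Algorithm | Main reason for visit, or final diagnosis |
| Fever without clinical source | Algorithm | No field named |
| Anemia | Prompted hemoglobin, cuvettes supplied | Routine tests and diagnosis |
| Malnutrition | Prompted weight and MUAC | Diagnosis; triage measurement unclear |
| Sex, age | Registration | Registration |

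Two of the nine modifiers in Section 10.3 are demographic and seven are clinical.

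**2. Can the observed surveys stand in?** Section 3.4.1 gives 18 facilities × 25 consultations = 450, which reproduces the stated total. Half the facilities are controls, so 9 × 25 = 225 consultations per arm per survey. Against 17,100 planned per arm, 225 / 17,100 = 1.3%.

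Precision for the difference in malaria testing needs figures the documents do not give. Assume a febrile share f of 50% to 90%, an ICC of 0.05 to 0.20 and 50% to 80% tested (p). With m = 25f febrile children per facility, n = 9m per arm and design effect 1 + (m − 1) × ICC, the 95% half-width is 1.96 × √(2p(1 − p) × design effect / n).

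- Best case (f = 0.9, ICC = 0.05, p = 0.8): m = 22.5, n = 202.5, design effect 2.075, half-width 11 points.
- Worst case (f = 0.5, ICC = 0.20, p = 0.5): m = 12.5, n = 112.5, design effect 3.3, half-width 24 points.

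The surveys use one questionnaire in both arms, so they are a fair cross-check. They are too small for interaction tests, and observers record only what the health worker assessed.

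**3. How far could the testing percentage move?** Assumed throughout: 70% of febrile children are truly tested in both arms, fever is recorded for every tested control child, and for a share s of untested control children. The control figure then reads 0.70 / (0.70 + 0.30 × s):

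- s = 1: 0.70 / 1.000 = 70%
- s = 0.75: 0.70 / 0.925 = 76%
- s = 0.50: 0.70 / 0.850 = 82%
- s = 0.25: 0.70 / 0.775 = 90%

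Identical practice would then show as a 6- to 20-point deficit for ePOCT+. If fever recording in controls were unrelated to testing, this bias would vanish.

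**The case against.** The strongest reply is that the deciding document is missing. The sentence on control tablets refers to Appendix 1, whose case report forms were not in the supplied text. The synopsis says the control application captures outcome-related data, and malaria testing in febrile children is an outcome, so a fever item may exist. The word limiting control tablets to demographics is also loose, since the next paragraph adds further fields. Section 8.1.2 does not restrict vital signs to intervention facilities, and Section 8.1.6 mentions staff engaged in triage in both arms. Section 7.1 marks some measures as intervention-only, so the authors did consider availability by arm. Section 10.3 defers detail to an analysis plan, and SAP Section 5.2.1 refers to a separate Phase 1 SAP. Section 10.3 also concedes low power for the interactions.

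Much of this stands. A reader might infer that control tablets hold no fever or symptom information at all, or that the malaria outcome cannot be measured in controls. The documents do not support either: main reason for visit, test results and diagnoses are recorded everywhere, surveys observe both arms, and the forms are unseen. Nor are all seven modifiers beyond repair, since the four complaint-based ones could be built alike in both arms from the main reason for visit.

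Two things do not yield. The protocol body names no common source, and its sections point in different directions. A fever item on the form would also not make anemia detection equal when the tests and prompts differ by arm. The supplied SAP does not help: it covers the Phase 2 medAL-mentor study, in which both arms use ePOCT+.

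**Conclusion.** The concern holds as a problem of unequal ascertainment on the protocol's description. It affects one named secondary outcome and the clinical part of the effect-modification plan. It is firmest for anemia and probable for malnutrition, where detection depends on arm. For fever and the complaint-based modifiers it is conditional on what the Appendix 1 forms contain.

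The size cannot be known from the documents. The 76% to 90% reading against a true 70% rests wholly on assumed recording rates and on fever being noted more often in tested children. It illustrates sensitivity and does not estimate bias.

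A reader might extend this to the main result. The text gives no ground for that: cure comes from the day 7 call or home visit, and antibiotic prescription comes from the closing screen used in both arms.

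**What to change.** 1. Reconcile the synopsis (Procedures and measurements) with Sections 8.1.2, 8.1.3 and 8.1.7 against the Appendix 1 forms. State whether the triage module and any fever or temperature field are on control tablets.
2. In Sections 7.1 and 10.3, define fever and the respiratory, gastrointestinal, skin and ear/throat modifiers, for every between-arm analysis, from one source recorded the same way in both arms before the consultation. The registration main reason for visit already qualifies. It misses fever accompanying another main complaint, so the outcome should be labelled accordingly.
3. If the forms lack them and capture can still change, add a few common tick-boxes to the registration module in both arms: fever in this illness, cough or breathing difficulty, vomiting or diarrhea, skin, ear or throat. SAP Section 2.1 already reports preliminary Phase 1 findings, so this may be too late for Phase 1, and items 2 and 4 would then carry the correction.
4. Report anemia, malnutrition and fever without source descriptively rather than as arm interactions, unless the forms show identical pre-consultation capture.

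The cost is a few sentences of protocol text and, if item 3 is used, about five fields. The downside of item 3 is slightly longer registration and a mild prompt in control facilities.
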